[figure not shown]

Official Title: Effect of supplementation with *Euterpe edulis* on the physical and mental performance of healthy men submitted to physical exercises

Ethical committee Protocol No: 6.202.888

Study protocol

1. Type of study

This is a clinical study, double blind, with the purpose of offering the juice of *E. edulis*, daily for 4 weeks before the day of the final evaluation, compared to the control. There will be about 40 men, aged 19 to 30 years, who perform regular physical exercises, in total of 150 min per week, at a minimum of 3 months.

2. Experimental Protocol

The men will be randomized into two groups, called GJ who will receive the sample and GP who will receive the placebo. The sample consists of 250 mL of juçara juice and the placebo which is 250 mL of water with pectin and natural dye. Research subjects will maintain their exercise routine, as well as fill out a food diary that will be sent electronically. The research will be for 11 days, and on day 1 (D1) of the research he will have the blood collected. On day 11 of the D11 survey, at time zero he will have the blood collected, and then consume the sample or the placebo. Two hours after he will be subjected to the battery of exercises, following 1. Dorsal dynamometer, 2. shoulder dynamometer, 3. manual dynamometer, 4. ergospirometry + electrocardiogram + digital lactate, 5. jump test for 1 min (amounts of jumps), 6. Pollock abdominal test and 7. functional mobility test. At the end, the blood will be collected, and a psychological form will be applied. After 2 and 7 days of physical exercise will be applied visual pain test.

3. The size of the sample

The calculation of the sample of patients for this study was performed using the software G*Power3.1.9.7 (Public domain). Considering the alpha value equal to 0.05 and the power of test $1 - \beta$ as 95% (0.95, that is, determining that the probability of type II error (β) should not be greater than 5%), the value of 20 patients was reached.

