The selection will be simple random probabilistic from a total population of patients who fit the inclusion criteria. Among the inclusion criteria are: being male, aged between 19 and 30 years and practicing physical exercises regularly for at least 3 months. Among the exclusion criteria are people who have motor problems, cardiovascular changes, have type I and II diabetes, smokers, athletes, cognitive deficits, and psychomotor disorders. Each patient will be evaluated at the beginning of the exercise and at the end of the exercise. Patients were randomly divided into 2 groups: treatment with placebo product and with the supplement of *E. edulis*.

4. Ethical issues

The study will be conducted after approval by the Ethics Committee on Research with Human Beings of the Vila Velha University and conducted in accordance with the Declaration of Helsinki. The clinical study will also be registered with REBEC, and will only be initiated after all ethical approvals. All participants will sign a written agreement (ICF).

As for the risks, in a previous study with 39 participants, none presented pictures of allergy or gastric or intestinal intolerance to JFJ and as a benefit, such a study demonstrated a positive effect on the acute adaptive inflammatory response (MENDES et al., 2021).

5. Inclusion criteria

Among the inclusion criteria are:

- Being male
- Aged between 19 and 30 years old
- Practicing physical exercises regularly for at least 3 months

6. Exclusion Criteria

Men who use:

- Steroids
- Anabolics
- Taurine
- BCCA
- Exogenous supplementation

7. Removal criteria

Among the exclusion criteria are people who have:

- Motor problems
- Cardiovascular changes
- Have type i and ii diabetes
- Smokers
- Athletes
- Cognitive deficits
- Psychomotor disorders.

Each patient will be evaluated at the beginning of the exercise and at the end of the exercise. Patients will be randomly divided into 2 groups: treatment with a placebo product and with an E. edulis supplement.

8. Intervention

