On day 11 of the D11 survey, at time zero he will have the blood collected, and then consume the sample or the placebo. Two hours after he will be subjected to the battery of exercises, following 1. Dorsal dynamometer, 2. shoulder dynamometer, 3. manual dynamometer, 4. ergospirometry + electrocardiogram + digital lactate, 5. jump test for 1 min (amounts of jumps), 6. Pollock abdominal test and 7. functional mobility test. At the end, the blood will be collected, and a psychological form will be applied. After 2 and 7 days of physical exercise will be applied visual pain test.

9. Preparation of Juçara juice

The preparation will be obtained with the same methods already well established in previous studies (SCHULZ et al., 2016.; MENDES et al., 2021). Participants will receive 250 ml of water + purple dye + pectin (control) or commercial samples of juçara (*E.edulis*) refrigerated to 4°C to 10°C, per day, for 10 days, and on the 11th will be the exercise and on this day will be administered the juice of the juçara 2 h before on the day of the monitored exercise. The chemical characterization of *Euterpe edulis* will be with at least 350.0 + or - 17.5 mg of total phenolics (gallic acid equivalent), 186.0 + or - 7.5 mg of total monomeric anthocyanins (cyanidin 3-glycoside), 0.73 + or less 0.01 g of proteins, and 2.75 + or - 0.03 g of lipids (ether extract). During the 10 days of previous treatment, maintain the routine of physical exercises.

10. Values evaluated

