10.6 Subjective analysis of fatigue

A questionnaire will be developed about the subjective perception of patients about the effects of the treatment employed in the recovery of muscle fatigue. The questions will be based on the Chalder scale and the International Short-Form Physical Activity Questionnaire (IPAQ-SF) (LEE et al., 2011). However, the feeling of improvement or not of physical fatigue after exercise will be the focus of the preparation of a new and unprecedented questionnaire

11. Statistical analysis

The results will be expressed as mean \pm SEM (standard error of the mean). Statistical analysis will be performed by one-way analysis of variance (ANOVA) (repeated measures), followed by Tukey's post hoc test, using the Prism software (Prism 6.0, GraphPad Software, Inc., San Diego, CA, USA). The differences will be considered significant when $p < 0.05$.

REFERENCES

ARCURI, J. F. et al. Validity and Reliability of the 6-Minute Step Test in Healthy Individuals: A Cross-sectional Study. **Clinical Journal of Sport Medicine**, v. 26, n. 1, p. 69-75, Jan. 2016.

BUTCHER, J. T. et al. Effect of myostatin deletion on cardiac and microvascular function. **Physiological Reports**, v. 5, n. 23, e13525, Dec. 2017.

CABARKAPA, D. et al. Position-specific differences in countermovement vertical jump force-time metrics in professional male basketball players. **Front Sports Act Living**, v. 20, n. 5, p. 1218234, Jul. 2023.

CARDOSO, A.L. et al. An Update on the Biological Activities of *Euterpe edulis* (Juçara). **Planta Médica**, v. 84, n. 8, p. 487-499, may., 2018.

CARROLL, T. J.; TAYLOR, J. L.; GANDEVIA, S. C. Recovery of central and peripheral neuromuscular fatigue after exercise. **Journal of Applied Physiology**, v. 122, n. 5, p. 1068-1076, May. 2017.

ELY, M. R. et al. A single dose of histamine-receptor antagonists before downhill running alters markers of muscle damage and delayed-onset muscle soreness. **Journal of Applied Physiology** v. 122, n. 3, p. 631-641, mar. 2017.

FANG, P. et al. Adipose-Muscle crosstalk in age-related metabolic disorders: The emerging roles of adipo-myokines. **Ageing Research Reviews**, v. 84, p. 101829, Feb. 2023.

FELZENSZWALB, I. et al. Toxicological evaluation of *Euterpe edulis*: a potential superfruit to be considered. **Food and Chemical Toxicology**, v. 58, p. 536-44, Aug. 2013.

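### No primary outcome and no adjustment across roughly 26 to 30 outcomes, each open to being called significant at p < 0.05

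*Combined protocol and SAP*

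**What the plan says.** Section 11 is the whole analysis plan. Results are summarised as mean and SEM, and the analysis is "performed by one-way analysis of variance (ANOVA) (repeated measures), followed by" Tukey's post hoc test. The decision rule is then "The differences will be considered significant when" p is below 0.05. No outcome is singled out.

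Nothing elsewhere fills the gap. Section 10 lists the measurements without ranking them. Section 3 gives alpha 0.05 and power 95% and says "the value of 20 patients was reached", but names no outcome, effect size, SD or test, and does not say whether 20 is per arm or in total. Section 4 adds "The clinical study will also be registered with REBEC", but that record is not part of these documents.

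The title promises an effect "on the physical and mental performance of healthy men submitted to physical exercises". Sections 2 and 8 list the D11 battery: three dynamometers, then "ergospirometry + electrocardiogram + digital lactate, 5. jump test for 1 min (amounts of jumps), 6. Pollock abdominal test" and a functional mobility test, followed by a psychological form and later pain ratings. For the first day, Section 2 says only "on day 1 (D1) of the research he will have the blood collected".

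**The concern.** A two-arm, placebo-controlled trial with a stated alpha and power reads as confirmatory, and nothing in the text calls it exploratory. Yet the plan does not say which result decides whether the juice improves physical performance, or which decides mental performance. With one p < 0.05 rule over a long list, some outcome is likely to cross the line by chance, and nothing in these documents stops that outcome from being presented as the finding.

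The planned ANOVA makes this worse. A one-way repeated-measures ANOVA has a single factor and defines no GJ-GP contrast, so the deciding comparison is unspecified even within one outcome.

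**Working it through.** **The plan's own figure.** The documents state no error rate across outcomes, so there is none to reproduce. The 20 in Section 3 cannot be reproduced without an effect size. Solving back with a two-sided 5% two-sample t-test at 95% power, 20 per arm implies a difference of 1.17 SD and 10 per arm implies 1.71 SD. Neither points to an outcome.

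**Counting outcomes** (a reading of the lists, not a bound):

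- simple reaction A1-A3 (10.1): 3
- choice reaction B1-B3 (10.2): 3
- dynamometers: 3
- ergospirometry: 1
- jump, abdominal and functional mobility tests: 3
- psychological form, pain, fatigue questionnaire (Sections 2 and 10.6): 3
- markers in the last paragraph of 10.3 (lactate, CK, TAC, testosterone, cortisol, GH, IL-6, IL-8, IL-10, TNF-alpha): 10

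The sum is 3+3+3+1+3+3+10 = 26. Adding IL-1 beta, MCP-1, adiponectin and adhesion molecules, named earlier in 10.3, gives 30. Counting the step test, plank test, ECG and digital lactate separately gives 34, though some may duplicate listed items and no ECG variable is defined.

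**Chance of at least one false benefit.** Assumptions: no true effect; one two-sided 5% GJ-GP test per outcome, so 2.5% in the benefit direction; a common correlation ρ, positive in the benefit direction. None of these is in the documents.

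- Independent: 1 − 0.975^k. For k = 26, 1 − 0.975^26 = 0.482.
- Correlated: 1 − ∫ φ(u) Φ((1.96 − √ρ·u)/√(1−ρ))^k du, integrated numerically.

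| Outcomes k | Independent | ρ = 0.5 | ρ = 0.7 |
|---|---|---|---|
| 1 | 2.5% | 2.5% | 2.5% |
| 26 | 48.2% | 23.9% | 16.0% |
| 30 | 53.2% | 25.5% | 16.9% |
| 34 | 57.7% | 26.9% | 17.7% |

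At ρ = 0.9 the figure is still 8.3% (26) to 8.6% (30). Simulated t-tests at ρ = 0.5, with 10 or 20 men per arm and 26 or 30 outcomes, gave 24.6% to 26.6%. The chance of a significant difference in either direction, for 26 to 34 outcomes, is 73.6-82.5% (independent), 47.5-53.5% (ρ = 0.5) or 32.1-35.4% (ρ = 0.7).

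**A reading kinder to the plan: Tukey over all group-by-time cells.** Take 20 per arm and treat cells as independent.

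- Two times: q(4, 76) = 3.715; 3.715/√2 = 2.627; level per comparison 0.0104.
- Three times: q(6, 114) = 4.100; 4.100/√2 = 2.899; level per comparison 0.0045.

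False benefit after baseline, 26 to 30 outcomes:

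- Two times: 1 − (1 − 0.0104/2)^k = 13-15% independent; 7-8% at ρ = 0.5.
- Three times (two later comparisons each): 1 − (1 − 0.0045/2)^(2k) = 11-13% independent; about 6% at ρ = 0.5.

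**Where that reading cannot apply.** Eight outcomes are listed only on D11: three dynamometers, ergospirometry, jump, abdominal, functional mobility and the psychological form. This assumes that the beginning and end evaluation mentioned after the eligibility criteria adds no second battery. With two means, Tukey's critical value is q(2, 38)/√2 = 2.024 = t(0.975, 38), which is the ordinary t-test at 5%. For these eight alone, false benefit is 1 − 0.975^8 = 18.3% independent, 12.5% at ρ = 0.5 and 9.5% at ρ = 0.7. Putting these eight at 2.5% and the other 18 to 22 at the Tukey levels gives about 14% to 15% overall at ρ = 0.5.

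**The case against.** The strongest objection is that the 24% to 26% describes a test the plan does not contain. The plan specifies Tukey, and if that is run over every group-by-time cell the figure falls to about 6-8% at correlation 0.5. This is fair as far as it goes, and the percentage should be read as one point in a range. But that reading gives all outcomes a baseline that at least eight do not have; the mixed calculation returns to about 14-15%.

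The count is also soft. The psychological form and the fatigue questionnaire may be one instrument; 25 outcomes instead of 26 gives about 23.5% at correlation 0.5. A benefit direction is not stated for several markers, such as testosterone, cortisol and GH, and one common correlation across hormones, reaction times and jumps is a simplification. These points limit precision, not the conclusion.

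The planned registration might name a primary outcome. That cannot be checked here, so the absence is asserted only for these documents.

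Finally, a single physical primary leaves mental performance without a confirmatory test, and naming a primary leaves open what Section 3 was calculated for. Both points stand and are taken up in the fix.

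**Conclusion.** The concern holds and must be fixed. The documents name no primary outcome and contain no control across outcomes, so the trial's conclusion is undefined and its false-benefit chance exceeds the 2.5% of a single two-sided 0.05 test. With one GJ-GP test per outcome and correlation 0.5, that chance is 23.9% for 26 outcomes and 25.5% for 30. Across the readings and correlations shown, it runs from about 6% to above 50%. The exact figure depends on assumed correlations, an assumed contrast and our count of outcomes. The two textual facts do not.

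**What to change.** Before unblinding, amend Section 11 to:

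1. Name one primary outcome from measures already planned (for example one named dynamometer measure) and its assessment day. To match the title, the alternative is one physical and one mental primary (for example that measure and A3), tested with Holm at overall two-sided 0.05.
2. Compare GJ with GP directly by a two-sample t-test at two-sided 0.05 (or the Holm level), in place of the one-way repeated-measures ANOVA. Use ANCOVA on the baseline value only if the chosen measure is also taken at baseline; a dynamometer measure has no listed baseline.
3. Rest the efficacy conclusion on the primary outcome(s) only. Report all others as secondary or exploratory GJ-GP differences with 95% confidence intervals.
4. State the day of the reaction tests if one is chosen, since the plan gives none.
5. Say in Section 3 which outcome and difference the 20 refers to, and whether it is per arm or in total.

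The day of final evaluation must first be reconciled: Section 1 has supplementation "daily for 4 weeks before the day of the final evaluation", while Sections 2, 8 and 9 place the evaluation on D11.

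**Cost.** Mostly wording, plus the sample-size clarification; secondary results are no longer confirmatory. A single primary costs no power but leaves one half of the title unconfirmed. With two primaries, the difference detectable with 95% power at the first Holm step (alpha 0.025) rises from 1.17 to 1.27 SD with 20 per arm, or from 1.71 to 1.87 SD with 10 per arm.
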